### Secondary Hypotheses

1. Post-treatment subjective scores of comfort (VAS scale) for eyes with the cornea anesthetized are superior to eyes with the upper or lower lid margins anesthetized.
2. Comfort change from pre-treatment for eyes with the cornea anesthetized is superior to eyes with the upper or lower lid margins anesthetized.
3. Subjective scores of comfort (VAS scale) at lens removal are equivalent to baseline levels (i.e. immediately prior to lens application in the morning) when the cornea is anesthetized. An equivalence margin of 10 points will be used.

### Other Hypotheses

None.

## 3. TARGETED STUDY POPULATION

### 3.1. General Characteristics

Symptomatic contact lens wearers who report a CLDEQ-8 score of 20-37 will be recruited.

### **3.2. Inclusion Criteria**

Potential subjects must satisfy all of the following criteria to be enrolled in the study:

#### Inclusion Criteria after Screening

1. They are of legal age (18 years) and capacity of volunteer.
2. The subject must read, understand, and sign the STATEMENT OF INFORMED CONSENT and receive a fully executed copy of the form.
3. They must appear able and willing to adhere to the instructions set forth in this clinical protocol.
4. They have worn the same brand of soft spherical contact lenses for at least the previous three months, by self-report.
5. They are defined as 'symptomatic' contact lens wearers (CLDEQ-8 score of 20-37) with their habitual contact lenses.
6. They are willing to wear their lenses for approximately 14 hours on study days.
7. They have a wearable pair of spectacles, if applicable.
8. They agree not to participate in other clinical research for the duration of this study.

#### Inclusion Criteria after Baseline

9. They can attain high contrast logMAR visual acuity of 0.20 or better in their habitual contact lenses in each eye.

### **3.3. Exclusion Criteria**

Potential subjects who meet any of the following criteria will be excluded from participating in the study:

#### Exclusion Criteria after Screening:

1. They have an ocular disorder, which would normally contra-indicate contact lens wear.
2. They have a systemic disorder, which would normally contra-indicate contact lens wear.
3. They are using any topical medication such as eye drops or ointment.
4. They have had cataract or corneal refractive surgery.
5. They are pregnant or breast-feeding by self-report.
6. They have any infectious disease (e.g. hepatitis) or any immunosuppressive disease (e.g. HIV), by self-report.
7. They have any known hypersensitivity or allergic reaction to any of the known ingredients in the anesthetic.
8. They have a history of severe allergic reaction or anaphylaxis.
9. They have a history of cardiac disease or hyperthyroidism.
10. They have taken part in any other contact lens or care solution clinical trial or research, within two weeks prior to starting this study.
11. They are an employee or immediate family member of an employee of clinical site (e.g., Investigator, Coordinator, Technician).

## Exclusion Criteria after Baseline

12. They have any corneal distortion resulting from previous hard or rigid lens wear or have keratoconus.
13. They have grade 3 or greater of any of the following ocular surface signs which would contraindicate contact lens wear: corneal oedema, corneal vascularisation, corneal staining, tarsal conjunctival changes or any other abnormality which would normally contraindicate contact lens wear.

### **3.4. Enrollment Strategy**

Study subjects will be recruited from the University of Manchester, UK's subject database and/or utilizing Independent Ethics Committee (IEC) or Institutional Review Board (IRB) approved materials.

## **4. STUDY DESIGN AND RATIONALE**

### **4.1. Description of Study Design**

The study design is controlled, randomized, subject-masked, 3 treatment ×3 period, non-dispensing, contralateral study.

After a pre-screening assessment, eligible subjects will be invited to attend an initial visit. Subjects will be prescreened using the CLDEQ-8 questionnaire with their habitual lenses and those who are classified as symptomatic (CLDEQ-8 score of 20-37) will be scheduled for Visit 1.

At study Visit 1, subjects will be consented and screened for inclusion/exclusion criteria. If a subject is found to meet all eligibility criteria, they will be asked to attend Visit 2 which will take place on a different day. Subjects will be asked to wear their contact lenses early in the morning (at home) on the day of Visit 2 and to rate subjective comfort on a paper VAS scale immediately prior to lens application and 5 minutes post-application. They will be asked to attend the study visit having worn their habitual lenses for  $14 \pm 2$  hours. At Visit 2, one of three areas (upper lid margin, lower lid margin or cornea) will be anesthetized on one eye, whilst the fellow eye will receive a saline placebo treatment in the same location. The ocular surface region and treatment will be randomly assigned. The right eye will always be assessed first. Subjective comfort scores (VAS scale) will be collected prior to and following the treatment on each eye (5 and 10 minutes post-treatment). On the day of corneal treatment, VAS comfort scores will also be collected immediately after lens removal prior to treatment application. Subjects will be asked to return for Visit 3 on a different study day, again having worn their lenses for  $14 \pm 2$  hours and the same procedures as at Visit 2 will take place. The same procedures as for Visit 3 will be repeated for Visit 4. Visits 2-4 will be scheduled 1-14 days apart.

## **4.2. Study Design Rationale**

Crossover designs are a well-established cost-effective study design in which subjects are exposed to multiple treatments during different time periods. The study design allows for a direct and meaningful comparison of three anesthesia treatments. A minimum period of 24 hours between visits (i.e. between each treatment) was implemented to reduce any potential carry-over effect that may bias the results.

## **4.3. Enrollment Target and Study Duration**

A total of up to 20 subjects will be enrolled (informed consent signed) at a single clinical site (University of Manchester) in the UK, with a target of 15 to complete.

Subjects will be considered to be enrolled onto the study when they have signed the informed consent. A replacement subject will be enrolled if a subject discontinues from the study before completing the study visits.

Each subject will attend for four visits of up to 1 hour in duration. The study is expected to last approximately 5 months and include a 1-month enrollment period.

## **5. TEST ARTICLE ALLOCATION AND MASKING**

### **5.1. Test Article Allocation**

An ocular surface region (upper lid margin, lower lid margin or cornea) will be randomly allocated to each visit and a treatment (anesthesia or placebo) will be randomly allocated to each eye using a randomization scheme supplied by the study biostatistician. A single ocular region will be investigated at each visit and a single treatment will be applied to each eye at each visit. The clinical site will follow the randomization scheme provided and will complete enrollment according to the randomization list and will not pre-select or assign subjects. The assignment of the subjects must be performed at Visit 1. The following must have occurred prior to randomization:

- Informed consent has been obtained
- Subject meets all the inclusion / exclusion criteria
- Subject history and baseline information has been collected

The randomization scheme will be generated using the PROC PLAN procedure from the SAS Software Version 9.4 or higher (SAS Institute, Cary, NC).

The regions (upper lid margin, lower lid margin, or cornea) will be treated in a bilateral and random fashion using a Williams design with 3 regions and 3 periods. Each subject will be randomly assigned to one of six unique sequences (U/L/C, L/C/U, C/U/L, C/L/U, U/C/L, L/U/C). For each region within a sequence, the two treatments will be randomly assigned to the left and right eye (anesthesia left eye/placebo right eye or placebo left eye/anesthesia left eye).

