**SYNOPSIS**

Protocol Title	An investigation of the impact of localized topical anesthesia of the ocular surface on end-of-day contact lens discomfort.
Sponsor	JJVC, [name]
Clinical Phase	Development phase, phase 0
Trial Registration	This study will be registered on ClinicalTrials.gov
Test Article(s)	None (habitual contact lenses)
Wear and Replacement Schedules	Habitual lenses will be worn for 14 ± 2 hours on study days
Objectives	
Primary Objective To evaluate the effect of topical anesthesia of the upper lid margin, lower lid margin and cornea on end-of-day discomfort in symptomatic contact lens wearers.
 
Secondary Objective To determine the effect of contact lens removal on end-of-day discomfort in symptomatic soft contact lens wearers.

Study Endpoints	
Primary endpoint: Subjective scores of comfort (VAS scale) collected at various time points:
 
 
• Immediately prior to lens application
 
• 5 minutes after lens application
 
• 14 hours after lens application (i.e. pre-treatment)
 
• Immediately after lens removal prior to treatment application, only for the cornea.
 
• 5 minutes post-treatment
 
• 10 minutes post-treatment
 
 
Other observations: none.

Study Design	
This is a controlled, randomized, subject-masked, 3x3 crossover, non-dispensing, contralateral study. Twenty subjects will be recruited based on their scores (with their habitual lenses) from the Contact Lens Dry Eye Questionnaire-8 (CLDEQ-8 score of 20-37) and examined on four occasions:
 
Visit 1: Screening  Visit 2-4: At each study visit, an ocular region (upper lid margin, lower lid margin or cornea) will be anesthetized on one eye, whilst the fellow eye will receive a saline placebo treatment at the same ocular location. Subjective comfort scores (VAS scale) will be collected prior to and following the treatment on each eye.
 
See the flow chart at the end of the synopsis table for the schematic of the study visits and procedures of main observations (Figure 1).

Sample Size	Up to 20 eligible subjects will be enrolled into the study with a target of 15 to complete.
Study Duration	Five months
Anticipated Study Population	Habitual soft contact lens wearers aged 18 and above who are classified as symptomatic based on a CLDEQ-8 score of 20-37

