2.12	Right eye Application of topical treatment	
One ocular region (upper lid margin, lower lid margin or cornea) of the right eye will be anesthetized or will receive a saline placebo treatment, based on the randomization scheme.
 
The procedures will take place with the subject's lenses in situ when the lid margins are treated. When the cornea is anesthetized, the subject's habitual lens will be removed and immediately dosed with the anesthetic as outlined in SOP #54. The lens will not be spun to removed excess liquid and will not be soaked in any solution prior to re-insertion. The dosing/re-application procedure should take place as quickly as possible to avoid the lens from dehydrating excessively.
 
If any problems with the application of the treatment occur, subjects are eligible to repeat the visit on another day only once.
	Eurolens Research SOP #54
2.13	Right eye Subjective comfort	
Subjective comfort scores (vertical VAS scale) will be collected for the right eye after 5 and 10 minutes post-treatment.
 
For the cornea, the contact lens is removed and then reapplied as part of the treatment application procedures. Comfort scores will also be collected immediately (ideally within 30 seconds) after lens removal prior to treatment application.
	██████████
2.14	Left eye Application of topical treatment	The same ocular region (upper lid margin, lower lid margin or cornea) of the left eye will be anesthetized or will receive a saline placebo treatment, based on the randomization scheme.	Eurolens Research SOP #54

		
The procedures will take place with the subject's lenses in situ when the lid margins are treated. When the cornea is anesthetized, the subject's habitual lens will be removed and immediately dosed with the anesthetic as outlined in SOP #54. The lens will not be spun to removed excess liquid and will not be soaked in any solution prior to re-insertion. The dosing/re-application procedure should take place as quickly as possible to avoid the lens from dehydrating excessively.
 
If any problems with the application of the treatment occur, subjects are eligible to repeat the visit on another day only once.
	

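### The eye-allocation rule misprints its second option and states no left/right balance within region, although the right eye always goes first and the models list no eye term

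*Combined protocol and SAP*

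**What the plan says.** Section 5.1 sets out how the randomization scheme is to be built. Region order follows a Williams design with six sequences. For the eyes it says "For each region within a sequence, the two treatments will be randomly assigned to the left and right eye" and then lists two options in parentheses. The first puts anesthesia in the left eye and placebo in the right. The second is printed as "placebo left eye/anesthesia left eye". Earlier in the same section the rule is that "a single treatment will be applied to each eye at each visit".

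Other parts of the protocol describe the paired design consistently:

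- Section 4.1: the region "will be anesthetized on one eye, whilst the fellow eye will receive a saline placebo treatment in the same location".
- Synopsis: one eye is anesthetized "whilst the fellow eye will receive a saline placebo treatment at the same ocular location".
- Section 7.2, step 2.12: the region "of the right eye will be anesthetized or will receive a saline placebo treatment, based on the randomization scheme".
- Section 7.2, step 2.14: the same region "of the left eye will be anesthetized or will receive a saline placebo treatment, based on the randomization scheme".

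On order, Section 4.1 states "The right eye will always be assessed first". Steps 2.12 to 2.15 treat the right eye and collect its 5- and 10-minute scores before the left eye is treated. Section 5.1 names PROC PLAN as the tool but states no blocking or left/right balance for eye. Section 14.5 lists the fixed effects of both models. No eye or laterality term is among them, and the listed term *sequence of treatment* is not defined.

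**The concern.** The parenthesis in Section 5.1 is the only place that enumerates the two eye allocations, and the site must follow the list built from it. A specification that contradicts itself should not go to the programmer, even when the intention is plain.

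The lack of stated balance carries more statistical weight. Because the right eye always goes first, eye and order are a single factor. The left eye is scored later in the visit, after longer lens wear, in a study whose outcome is end-of-day comfort. If anesthesia falls mostly on one side within a region, any first-eye/second-eye difference is mixed into that region's treatment contrast. Superiority is declared when the lower confidence limit exceeds 0 in any one of three regions, and the differences considered in Section 14.2 are only 5 to 10 VAS points. A shift of one to three points is therefore not negligible.

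**Working it through.** **1. Does the misprint change the design?** Two products go to two eyes with one product per eye, so only two arrangements exist. One is printed correctly; the other must be placebo left, anesthesia right. A visit with nothing for the right eye could not be carried out at step 2.12. Each completer therefore still gives one anesthesia-minus-placebo difference per region, which is 15 pairs.

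**2. The plan's power figure.** Inputs from Section 14.2: difference 7.5, SD 15, intraclass correlation 0.8, 15 completers.
- SD of the difference = 15 × √(2 × (1 − 0.8)) = 9.49.
- Noncentrality = 7.5 × √15 / 9.49 = 3.06, with 14 df.
- Paired t power = 0.897 at one-sided 0.05, which is the Table 3 entry. At the stated two-sided 0.05 it is 0.812.

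The one-sided/two-sided discrepancy is a separate matter. Correcting the eye label changes neither number.

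**3. Chance of imbalance.** Assumption: an independent fair coin toss per subject and region, because no restriction is stated. With 15 completers:
- P(8:7) = 2 × 6435 / 32768 = 0.393.
- P(10:5 or worse) = 2 × (3003 + 1365 + 455 + 105 + 15 + 1) / 32768 = 0.302.
- P(11:4 or worse) = 2 × 1941 / 32768 = 0.118.
- At least one of three regions, treated as independent: 1 − (1 − 0.302)³ = 0.66 for 10:5 or worse, and 1 − (1 − 0.1185)³ = 0.315 for 11:4 or worse.

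**4. Effect on the estimate.** Let d be the right-minus-left (first-minus-second) comfort difference that would exist without treatment. With anesthesia in the right eye for k of 15 subjects, the unadjusted difference moves by d × (2k − 15)/15. That is 0.07d at 8:7, 0.33d at 10:5 and 0.47d at 11:4. The documents give no d. At a 10:5 split, d = 3, 5 or 10 gives a shift of 1.0, 1.7 or 3.3 points.

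**5. Bias or precision?** Under a fair toss 2k − 15 has mean 0 and variance 15, so the shift averages zero and has variance d²/15. The standard error of the unadjusted estimate is √((90 + d²)/15): 2.45 at d = 0, 2.57 at d = 3, 2.77 at d = 5. With an 8:7 split and an eye term it is √(6 × 1.004) = 2.45 whatever d is. The factor is 15²/(4k(15 − k)), which would be 1.125 at 10:5 and 1.278 at 11:4.

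**6. Effect on the test.** I simulated one region on its own: 15 differences, SD 9.49, superiority declared when the lower two-sided 95% limit exceeds 0, 200,000 trials per case. With a coin toss and no eye term, the false-positive rate under no treatment effect stayed at 0.024 to 0.026 for d from 0 to 10, against a nominal 0.025. Power at a true difference of 7.5:

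| Allocation and model | d = 3 | d = 5 |
|---|---|---|
| Coin toss, no eye term | 0.774 | 0.713 |
| Coin toss, eye term | 0.776 | 0.777 |
| 8:7 split, no eye term | 0.782 | 0.724 |
| 8:7 split, eye term | 0.805 | 0.805 |

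Balance alone gains little, because the order difference stays in the residual variance and keeps the interval wide. Balance and the eye term belong together.

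**The case against.** A reader might infer from the printed option that about half the visits would yield no pair, leaving 7 or 8 per region and cutting two-sided power from 0.81 to between 0.42 and 0.49. The documents do not support this. The governing clause of the same sentence, the one-product-per-eye rule, the Synopsis, Section 4.1 and steps 2.12 and 2.14 all exclude it. Only the correction of the text stands.

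On balance, the fair reply has five parts.

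- Silence about blocking does not show that there is none. The biostatistician's list is not in the documents and may be blocked. This stands, so the coin toss is labelled an assumption.
- Random assignment leaves the contrast unbiased over allocations. This also stands, and steps 5 and 6 of the check confirm it. A reading that the order effect systematically favors anesthesia is not supported.
- *Sequence of treatment* may encode the eye allocation. It may, but it is undefined, so it cannot be relied on.
- The change-from-pre-treatment analysis removes stable differences between the eyes. That is true, but both eyes are scored before the right eye is treated (step 2.11), so an effect of going second remains in the change.
- Fifteen completers cannot split evenly, and with up to 20 enrolled and replacement of dropouts, blocking will not guarantee balance among completers. This is correct, but blocking still makes a split such as 10:5 much less likely.

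The study is also described as a pilot and feasibility study. That limits the importance of the point, but the remedy costs almost nothing.

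**Conclusion.** Two modest points hold. First, the second eye allocation in Section 5.1 is misprinted. The intention is clear, and the number of pairs and their power do not change. Second, no left/right balance within region is stated, while eye is tied to order and the models list no defined term for it. If assignment is unrestricted, a 10:5 or worse split has probability 0.30 per region and shifts that region's unadjusted estimate by d/3 or more, in either direction. The type I error rate is not inflated. The loss is one of precision and of a clean reading of a single region's result. With SD 15, correlation 0.8 and a true difference of 7.5, balance plus an eye term is worth about 3 points of power at d = 3 and 9 points at d = 5. These values of d are assumptions, and if d is zero nothing is gained. This is a low-severity point that is worth settling before the list is produced.

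**What to change.** - In Section 5.1, correct the second option so that it assigns placebo to the left eye and anesthesia to the right eye.
- In the same section, state that the two eye options are allocated in permuted blocks within each region, and generate them in the same PROC PLAN step as the region sequences.
- In Section 14.5, add eye (equivalently, order of treatment within the visit) as a fixed effect in both models, and define *sequence of treatment* or drop it if eye replaces it.

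The cost is one word, a blocked list and one degree of freedom. In the simulation the eye term lowered power from 0.812 to 0.806 when d was zero and the split was 8:7. No extra subjects, visits or procedures are needed. The two allocation changes must precede generation of the list; the model change should be fixed before database lock.

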## 5.2. Masking

This is a single masked study, where subjects will be unaware of the treatment (anesthesia or placebo) applied to each eye, since the Investigator will be preparing the treatment out of sight of the subject. Investigators and clinical site personnel involved in the data collection will not be masked as to the identity of the treatment.

## 5.3. Procedures for Maintaining and Breaking the Masking

Study codes will not be used for masking.

## 6. STUDY INTERVENTION

### 6.1. Identity of Test Articles

None.

### 6.2. Ancillary Supplies/Products

Table 1: Ancillary Supplies

Solution Name/Description	Proxymetacaine hydrochloride 0.5% (local anesthetic)	0.9% w/v sodium chloride solution
Manufacturer	Chauvin Pharmaceuticals Ltd (a subsidiary of Bausch + Lomb)	Crest Medical Ltd (or alternative sponsor-approved product)
Preservative	None	None
Other distinguishing items (dye, packaging, approval status, etc.)	Single-use minims (0.5ml)	Single-use pods (20ml)

### 6.3. Administration of Test Articles

Not applicable.

### 6.4. Packaging and Labeling

Not applicable.

### 6.5. Storage Conditions

Not applicable.

### 6.6. Collection and Storage of Samples

No samples will be collected as part of the study procedures.

### 6.7. Accountability of Test Articles

Not applicable. Subjects will be using their habitual lenses.

## 7. STUDY EVALUATIONS

### 7.1. Time and Event Schedule

Table 2: Time and Events

Visit Information	Visit 0 Pre-screen	Visit 1 Screening and Baseline	Visit 2 Treatment region 1	Visit 3 Treatment region 2	Visit 4 Treatment region 3, Final Evaluation
Time Point		24 hours to 28 days from Visit 0	24 hours to 14 days from Visit 1	24 hours to 14 days from Visit 2	24 hours to 14 days from Visit 3
Estimated Visit Duration		45 minutes	1 hour	1 hour	1 hour
Phone/electronic consent	x				
Statement of Informed Consent		x			
Demographics		x			
Medical History/Concomitant Medications		x			
Habitual Contact Lens Information		x			
Inclusion/Exclusion Criteria		x			
Changes in concomitant medications, medical history and adverse events			x	x	x
CLDEQ-8 Questionnaire	x				
Len Application (prior & 5 min post) VAS			x	x	x
Entrance Visual Acuity		x	x	x	x
Slit Lamp Biomicroscopy		x	x	x	x
Eligibility	x	x			
Randomization		x			
Lens wear information			x	x	x
Patient reported ocular symptoms			x	x	x
Lens Fit Assessment			x	x	x
Pre-treatment VAS comfort score			x	x	x
Application of topical anesthetic/saline			x	x	x

Visit Information	Visit 0 Pre-screen	Visit 1 Screening and Baseline	Visit 2 Treatment region 1	Visit 3 Treatment region 2	Visit 4 Treatment region 3, Final Evaluation
Time Point		24 hours to 28 days from Visit 0	24 hours to 14 days from Visit 1	24 hours to 14 days from Visit 2	24 hours to 14 days from Visit 3
Estimated Visit Duration		45 minutes	1 hour	1 hour	1 hour
Post-treatment VAS comfort score			x	x	x
Contact lens removal			x	x	x
Slit Lamp Biomicroscopy			x	x	x
Exit Visual Acuity		x	x	x	x
Study Completion					x

